4.6 Product Handling

While at the sites, products used during the study will be kept in their packages until use and stored under temperature controlled conditions (See Section 4.2). All VLN products will be securely stored at the clinical sites, in areas which are locked and with restricted access. No special procedures are required for the safe handling of the UB products.

During ambulatory periods, subjects will be asked to keep the study products at room temperature.

The VLN cigarettes in this study do not have a specified shelf life. They were manufactured in March 2018.

5. STUDY PROCEDURES

5.1 Screening

Potential subjects will undergo Screening procedures to ensure that they meet the requirements for inclusion in the study within 28 days prior to their first study visit at the start of Week -1.

Screening procedures will include the following:

- Sign ICF
- Demographics
- Smoking/tobacco/nicotine product use history
- UB cigarette and flavor documentation, including taking a color photocopy of the front and back of the subject's UB cigarette pack along with a ruler
- Medical history
- Review of Concomitant Medications
- Standard physical examination including oral cavity and oropharynx
- Review of Inclusion/Exclusion criteria
- Clinical laboratory tests (clinical chemistry, hematology, urinalysis)
- HIV, HBsAg, and HCV serology
- Urine drug and alcohol screens
- Exhaled breath CO measurement
- Urine cotinine screen
- Vital signs
- Height, body weight, and BMI
- 12-lead ECG
- Serum pregnancy test for females
- Serum FSH for postmenopausal females
- Review of smoking and nicotine product restrictions
- VLN cigarette trial
- Begin AE recording after product trial
- Provide smoking cessation information

5.2 Baseline Visit (Start of Week -1)

Subjects will visit the clinic at the start of Week -1 at a time specified by the clinic. The following procedures will take place during this visit:

- Verification that inclusion and exclusion criteria have not been violated since Screening
- UB cigarette documentation
- Review of AEs and concomitant medication use
- Urine drug and alcohol screens
- Urine cotinine screen and eCO measurement
- Vital signs
- Symptom-driven physical examination, if applicable
- Body weight
- Serum pregnancy test for females
- Training on e-diary use
- Dispense canisters for used cigarette butt collection
- Review smoking and nicotine product use restrictions

5.3 Ambulatory Periods Between Clinic Visits

Subjects will be required to record their daily cigarette consumption in electronic diaries and to collect all used (both compliant and non-compliant) cigarette butts in the provided canisters. Subjects will receive reminder contact to return to the CRU. At each visit, concomitant medications and AEs will be reviewed.

5.4 Clinic Visits (End of Weeks -1, 2 and 6)

Subjects will check in to the clinic at the end of Weeks, -1, 2 and 6 at times specified by the clinic. Subjects will be housed in the clinic until after the 24-hour urine collection and other study procedures. The following procedures will take place during this visit:

- Verification that inclusion and exclusion criteria have not been violated since last visit
- UB cigarette documentation for subjects assigned to continue smoking UB cigarettes
- Urine drug and alcohol screens
- Vital signs
- Urine pregnancy test for females
- Review of AEs and concomitant medication use.
- Usual brand cigarette documentation (only at Week -1).
- Return canister with used cigarette butts for counting
- 24-hour urine collection for BoE analysis
- Plasma sample for cotinine analysis
- Blood sample for carboxyhemoglobin (COHb) analysis
- Daily recording of CPD in the e-diary.
- Completion of subjective effects questionnaires
- Puffing topography assessment (subset of subjects)
- Nicotine PK assessment (subset of subjects)

- Dispense new canister for collecting used cigarette butts during next ambulatory period, except at Week 6
- Review smoking and nicotine product use restrictions
- Test product dispensing for the following ambulatory period; except at Week 6

All subjects will have their personal belongings thoroughly checked at the start of these clinic visits.

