3. SUBJECT SELECTION

3.1 Inclusion Criteria

Potential subjects must fulfill all of the following inclusion criteria to be eligible for participation in the study.

1. Is a healthy adult male or female adult smoker, 26 to 65 years of age, inclusive, at Screening.
2. Has been a smoker for at least 5 years prior to Screening. Brief periods of non-smoking (e.g., up to 7 consecutive days due to illness, trying to quit, participation in a study where smoking was prohibited) during that time will be permitted at the discretion of the Investigator.
3. Reports smoking an average of 10 or more manufactured combustible cigarettes per day at Screening.
4. Usual brand (UB) of cigarette is a filtered king size cigarette (with an approximate length of 84 mm (\pm 3 mm)).
5. Has a positive urine cotinine (\geq 500 ng/ml) at Screening.
6. Has an exhaled CO $>$ 10 ppm at Screening.
7. If female, has a negative serum pregnancy test at Screening.
8. A female subject of childbearing potential must have been using one of the following forms of contraception and agree to continue using it through completion of the study:
 - hormonal (e.g., oral, vaginal ring, transdermal patch, implant, or injection) consistently for at least 3 months prior to Screening;
 - double barrier method (e.g., condom with spermicide, diaphragm with spermicide) consistently for at least 14 days prior to Screening;
 - intrauterine device for at least 3 months prior to Screening;
 - Essure[®] or similar nonsurgical sterilization procedure at least 6 months prior to Screening

- a partner who has been vasectomized for at least 6 months prior to Screening;
 - abstinence beginning at least 14 days prior to Screening and through the End of Study.
9. A female subject of non-childbearing potential must have undergone one of the following sterilization procedures at least 6 months prior to Screening:
- hysteroscopic sterilization;
 - bilateral tubal ligation or bilateral salpingectomy;
 - hysterectomy;
 - bilateral oophorectomy;
- Or be postmenopausal with amenorrhea for at least 1 year prior to Day 1 and follicle-stimulating hormone (FSH) levels consistent with postmenopausal status.
10. Willing to comply with the requirements of the study, including a willingness to use the test products.
11. Voluntary consent to participate in this study documented on the signed informed consent form (ICF).
12. Subject is not planning to leave the area during the course of the study.

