3.2 Exclusion Criteria

Subjects may be excluded from the study if there is evidence of any of the following criteria at Screening, start of Week -1 (first clinic visit), or during the study as noted, in the opinion of the Investigator.

1. History or presence of clinically significant gastrointestinal, renal, hepatic, neurologic, hematologic, endocrine, oncologic, urologic, pulmonary (especially bronchospastic diseases and asthma), immunologic, psychiatric, or cardiovascular disease, or any other condition that, in the opinion of the Investigator, would jeopardize the safety of the subject or impact the validity of the study results.
2. Clinically significant abnormal findings on the physical examination, medical history, ECG, or clinical laboratory results, in the opinion of the Investigator.
3. Positive test for human immunodeficiency virus (HIV), hepatitis B surface antigen (HBsAg), or hepatitis C virus (HCV).
4. An acute illness (e.g., upper respiratory infection, viral infection) requiring treatment with prescription medication(s) within 14 days prior to Screening or first clinic visit.
5. Fever (>100.5°F) at Screening or first clinic visit.
6. Body mass index (BMI) greater than 40.0 kg/m² or less than 18.0 kg/m² at Screening.
7. History of drug or alcohol abuse or has used medical/recreational marijuana within 12 months of Screening.
8. Diabetes mellitus that is not controlled by diet/exercise alone, in the opinion of the Investigator.
9. Seated heart rate is lower than 40 bpm or higher than 99 bpm at Screening, unless deemed not clinically significant by the PI.

10. Seated systolic blood pressure <90 mmHg or >150 mmHg, diastolic blood pressure <40 mmHg or >95 mmHg at Screening, unless deemed not clinically significant by the PI.
11. Positive urine screen for drugs of abuse or alcohol at Screening or at the first clinic visit.
12. Female subjects who are pregnant, lactating, or intend to become pregnant from Screening through the End of Study.
13. Use of medications known to interact with cytochrome p450 2A6 (including, but not limited to, amiodarone, desipramine, isoniazid, ketoconazole, miconazole, phenobarbital, rifampin, tranylcypromine, methoxsalen) within 3 months prior to Screening and throughout the study.
14. Use of inhalers to treat any medical condition within 3 months prior to Screening and throughout the study.

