15. Use of nicotine-containing products other than factory manufactured cigarettes [e.g., roll-your-own cigarettes, e-vapor products, bidis, snuff, nicotine inhaler, pipe, cigar, chewing tobacco, nicotine patch, nicotine spray, nicotine lozenge, or nicotine gum] within 28 days prior to Screening.
16. Use of any prescription smoking cessation treatments, including, but not limited to, varenicline (Chantix[®]) or bupropion (Zyban[®]) within 3 months prior to Screening.
17. Self-reported puffer/non-inhaler (*i.e.*, a smoker who draws smoke from the cigarette into the mouth and throat but does not inhale).
18. Planning to quit smoking during the study period or postponing a quit attempt in order to participate in the study.
19. Plasma donation within 7 days prior to Screening or at any time during the study.
20. Donation of blood or blood products (with the exception of plasma as noted above), had significant blood loss, or received whole blood or a blood product transfusion within 56 days prior to Screening.
21. Participation in a previous clinical study for an investigational drug, device, biologic, or tobacco product within 30 days prior to Screening.
22. Subject or a first-degree relative (*i.e.*, parent, sibling, child) is a current or former employee of the tobacco industry or a named party or class representative in litigation with the tobacco industry.
23. Subject or a first-degree relative (*i.e.*, parent, sibling, child) is a current employee of the clinic sites.

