3.5 Subject Early Discontinuation or Withdrawal

Subjects will be advised that they are free to withdraw from the study at any time. In addition, subject participation in this trial may be discontinued for any of the following reasons.

- Adverse event
- Lost to follow-up
- Non-compliance with study procedures
- Protocol violation
- Pregnancy for female subjects
- Study terminated by Sponsor, US Food and Drug Administration (FDA), or other regulatory authorities
- Withdrawal of consent
- Investigator's discretion, including a severe laboratory abnormality or other medical condition that indicates to the Investigator that continued participation is not in the best interest of the subject

Subject's e-diary completion rates will be checked at each study visit. If the percentage of days on which the e-diary was completed is below 70%, subjects may be withdrawn from the study.

Other protocol deviations/violations should not lead to subject withdrawal unless they indicate a significant risk to the subject's safety or jeopardize the scientific integrity of the study.

If premature withdrawal from the study occurs for any reason, the Investigator must determine the primary reason and record this information in the case report form (CRF). Additionally, subjects withdrawing after study product use will undergo all end-of-study safety procedures as feasible and as deemed necessary by the Investigator.

A subject withdrawn from the study due to any AE or clinically significant abnormal laboratory test values will be evaluated by the Investigator or other monitoring physician and will be treated and/or followed up until the symptoms or values return to normal or acceptable levels or until lost to follow-up, as appropriate in the opinion of the Investigator.

Subjects withdrawing or removed from this study cannot re-enter.

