6.2 Analysis Populations

The statistical analysis will be based on separate, hierarchically organised, analysis populations defined as the following:

Safety population. All subjects who smoked at least one VLN cigarette

Intent-to-treat (ITT) population. All subjects who had at least one valid recording of cigarette consumption (a period of one week of >70% completion of their e-diary).

Per-protocol (PP) population. All subjects who had valid recording of cigarette consumption and completed the study according to the protocol. Data will be excluded from this population:

- If a subject self-reports smoking a significant number of cigarettes other than those which they have been assigned according to the protocol, or if this is apparent following checking of their collected used cigarette butts
- If there is a significant discrepancy between the self-reported number of cigarettes smoked per day and the number of used cigarette butts collected
- Based on a published method of assessing compliance (6). After switching, subjects will be deemed non-compliant if their ratio of [plasma cotinine/CPD VLN]/[plasma cotinine/CPD baseline] exceeds 0.2.

If it is determined that a subject is pregnant during the study, the pregnant subject's data will be listed but excluded from all PK parameter summaries.

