5. ANALYSIS POPULATIONS

The statistical analysis will be based on separate, hierarchically organized, analysis populations defined as the following:

Safety population: All enrolled subjects who smoked at least one cigarette of any type. This population will be used for safety analysis.

Intent-to-treat (ITT) population: All subjects who had at least one valid recording of cigarette consumption (a period of one week of >70% completion of their e-diary).

Per-protocol (PP) population: All subjects who had valid recording of cigarette consumption and completed the study according to the protocol. Data will be excluded from this population:

- If a subject self-reports smoking a significant number of cigarettes other than those which they have been assigned according to the protocol, or if this is apparent following checking of their collected used cigarette butts
- If there is a significant discrepancy between the self-reported number of cigarettes smoked per day and the number of used cigarette butts collected
- If a subject is non-compliant based on a published method of assessing compliance. After switching, subjects will be deemed non-compliant if their ratio of [plasma cotinine/CPD VLN]/[plasma cotinine/CPD baseline] exceeds 0.2.

If it is determined that a subject is pregnant during the study, the pregnant subject's data will be listed but excluded from all PK parameter summaries.

PK Population: Subjects in the PP or ITT population who have at least one PK blood draw resulting in at least one quantifiable plasma nicotine concentration. This population will be used for PK analysis (secondary endpoint analysis) and all available data will be included in the concentration and PK parameter tables to the extent possible.

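### A subject who quits smoking on VLN has no clearly stated place in the per-protocol set, so the largest possible falls in CPD can be lost from the primary analysis

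*Protocol*

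**What the plan says.** **Eligibility.** Protocol 5.4 lists "Verification that inclusion and exclusion criteria have not been violated since last visit" among the procedures at the end of Weeks -1, 2 and 6. Protocol 5.5 has the same item at Week 4. Three of these four checks (Weeks 2, 4 and 6) fall after the switch on Day 1 of Week 1. Exclusion criterion 18 in Protocol 3.2 reads "Planning to quit smoking during the study period or postponing a quit attempt in order to participate in the study". The lead-in to 3.2 makes exclusion permissive and lets criteria apply at Screening, "start of Week -1 (first clinic visit), or during the study as noted, in the opinion of the Investigator". Protocol 3.5 adds: "Other protocol deviations/violations should not lead to subject withdrawal unless they indicate a significant risk to the subject's safety or jeopardize the scientific integrity".

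**Compliance.** Under Protocol 6.2, PP membership requires completion according to the protocol. It also applies a cotinine rule: "After switching, subjects will be deemed non-compliant if their ratio of [plasma cotinine/CPD VLN]/[plasma cotinine/CPD baseline] exceeds 0.2". SAP 5 repeats the rule. Neither document says what happens when CPD on VLN is zero.

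**Analysis.** Protocol 6.3.7 and SAP 7.3 run the paired CPD tests on PP. SAP 7.2 gives ITT descriptive statistics only. Protocol 6.3 does not impute missing data and summarizes on reduced denominators.

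**The concern.** The hypothesis in Protocol 1.3 is that daily consumption falls after the switch, and the largest possible fall is to zero. Quitting is foreseeable here. Protocol 1.1 presents nicotine reduction as a way to lessen addiction and help cessation, and Protocol 5.13 tells every subject at Screening that quitting is the best course.

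Nothing in either document says that such a subject remains in follow-up and in PP at 0 CPD. There are two ways to lose one:

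- The site reads a new decision to quit as a breach of criterion 18. The subject is then withdrawn, or is judged not to have completed according to the protocol.
- The compliance ratio has no value, and the subject is treated as not evaluable for PP.

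Either would be an exclusion that depends on the primary outcome, in an open-label study where site staff know the product.

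**Working it through.** **1. Does criterion 18 apply after the switch?** The text points both ways.

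*For continued application:* 5.4 and 5.5 cover the criteria as a whole with no exemption. Criterion 18 has no Screening limit, whereas inclusion 3 has one: "Reports smoking an average of 10 or more manufactured combustible cigarettes per day at Screening". A fall in CPD therefore does not breach inclusion 3, but a new plan to quit meets the words of criterion 18.

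*For entry only:* in-study application is restricted to criteria that note it, and criteria 12, 13, 14 and 19 carry their own in-study time limits. In 18, the reference to the study period dates the planned quit and not the assessment. Its second half, about postponing a quit attempt, makes sense only at entry. Protocol 5.12.2 asks about quit plans as part of product-use history. The Summary of Study Events places both that history and the criteria review at Screening only.

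The entry-only reading is the better one, but the visit instructions do not state it.

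**2. The ratio.** Let C1 and B be cotinine and CPD at baseline, and C2 and v the values on VLN.

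- R = (C2/v) / (C1/B). At v = 0 this is a division by zero, whatever the cotinine.
- R > 0.2 is the same as C2/C1 > 0.2 × v/B.
- If VLN cotinine scales with VLN CPD at a fraction f of the usual-brand yield per cigarette, then C2 = f × (C1/B) × v and R = f at every v > 0. With f = 0.05 (assumed), R = 0.05 at 15 CPD and also at 1 CPD.

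The rule is therefore undefined at zero, and a low CPD above zero does not by itself fail it.

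**3. The plan's own figure.** Protocol 6.1.1 gives 50 subjects per VLN group for a fall of 3 CPD at 80% power and alpha 0.05. It states no SD of the paired difference, so 50 cannot be reproduced. Working backwards with the paired t-test, 50 implies an SD of 7.42 (two-tailed, as in the Protocol) or 8.41 (one-tailed, as in SAP 4.1). This point uses only the 3 CPD.

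**4. Size of the loss.** Assume that a share q quits from baseline B, the rest fall by 3 CPD, and every quitter is lost.

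- True mean fall = (1 - q) × 3 + q × B = 3 + q(B - 3)
- Fall reported without quitters = 3
- Understatement = q(B - 3)

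| q | B = 15 | B = 20 |
|---|---|---|
| 2% | 0.02 × 12 = 0.24 | 0.02 × 17 = 0.34 |
| 5% | 0.05 × 12 = 0.60 | 0.05 × 17 = 0.85 |
| 10% | 0.10 × 12 = 1.2 | 0.10 × 17 = 1.7 |

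The planned 3 CPD may instead be the overall fall, quitters included. Those who remain then fall by (3 - qB)/(1 - q), and the understatement is q(B - 3)/(1 - q). At 5% that is 0.60/0.95 = 0.63 to 0.85/0.95 = 0.89, so the choice matters little.

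**The case against.** **No passage orders withdrawal of a quitter.** This stands. The discontinuation reasons in Protocol 3.5 do not name quitting, exclusion is permissive, and 3.5 discourages withdrawal for other deviations. A reader might infer from 5.4 and 5.5 that the Protocol requires quitters to be removed; it does not. What remains is that the visit text contains no exemption, the decision is left to the investigator, and 3.5 does not settle PP status.

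**An undefined ratio does not exceed 0.2, so a literal reader could keep the subject.** Also fair. A reader who needs a computed ratio to establish compliance would drop the same subject, and the documents do not choose between the two.

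**A reader might infer that the ratio removes subjects because their CPD fell.** The algebra in step 2 does not support this. Above zero CPD the ratio rises only when some cotinine does not scale with recorded VLN CPD, and unexplained nicotine is what the rule exists to detect.

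**A reader might also want a cut on cotinine alone in place of the ratio.** The case for that is weak. I ran an illustrative simulation, all inputs assumed: baseline CPD normal with mean 18 and SD 6, limited to 10 to 40; VLN CPD averaging 83% of baseline, log-SD 0.3 or 0.5; 60% of subjects adding non-assigned cigarettes, exponential with mean 2 or 3 a day; VLN intake 4% of usual brand. A subject is excluded only if non-assigned use exceeds 0.16 of VLN CPD (from 0.2 - 0.04), so no subject without such use was excluded. The CPD endpoint in Protocol 2.2 counts non-assigned smoking. On that count the all-subject fall was 1.3 to 1.9 CPD. It was 1.6 to 2.35 among subjects kept by the present rule and 2.6 to 2.8 under a cotinine-only cut of 0.2. The cotinine-only cut was further from the all-subject value in all four scenarios.

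**The effect is not confined to the VLN groups.** The visit re-check also covers subjects who stay on their usual brand. Only the ratio is specific to the period after switching.

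**Conclusion.** The concern holds in a limited form. The Protocol does not exempt criterion 18 from the post-switch checks, and the compliance ratio has no value at zero VLN CPD. Since inference on CPD rests on PP alone, a subject who quits on VLN can be lost from the primary result.

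The loss would understate the fall: by 0.60 to 0.85 CPD if 5% quit from 15 to 20 CPD, and by 0.24 to 1.7 CPD over quit rates of 2% to 10%, against a planned 3 CPD. These figures assume the quit rate and the baseline CPD, neither of which the documents give, and that every quitter is lost; they are upper limits for each quit rate and baseline when the others fall by 3 CPD.

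The bias works against the stated hypothesis, and such subjects can still appear in the ITT descriptive tables. It is therefore a gap to close before database lock and not a threat to a positive finding. It remains an exclusion that depends on the outcome, and it affects the size of the reported reduction.

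**What to change.** 1. In Protocol 5.4 and 5.5, state that criterion 18 is assessed only up to product assignment. State also that a later decision to quit, or cessation itself, is an outcome and neither an eligibility breach nor a PP deviation. The subject stays in follow-up and in ITT and PP with CPD as recorded, including 0.
2. In Protocol 6.2 and SAP 5, state that the cotinine/CPD ratio is not applied when VLN CPD is zero, and that compliance is then judged on the e-diary, the butt count and plasma cotinine together.
3. Keep the published ratio unchanged for all other subjects.

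The cost is a Protocol clarification and a few lines in the SAP. No new data, visits or subjects are needed, because diary, butts and cotinine are already collected.
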